- Compare the effectiveness of PRGF Vs CGF.

Patients and Methods

Patient selection

this study will be conducted on 20 patients indicated for immediate implant placement in the maxillary anterior region. After approval from the ethical committee, the entire patients will be recruited from the outpatients' clinic of the Oral Medicine, Oral Diagnosis, and Periodontology Department. Faculty of Dentistry, Minia University.

Inclusion criteria:

1. Selected patients of both sexes are 20-40 years old.
2. Patients are systemically healthy based on questionnaire dental modification of Cornell index.
3. Gingival health according to the new classification system (2017)
4. The recipient site of the implant is free from any pathological conditions.
5. Class II extraction socket according to Chang's classification system
6. Adequate interocclusal space to accommodate the available restorative components.
7. Adequate native/apical bone to achieve primary implant stability.

Exclusion criteria:

1. Pregnant female.
2. Parafunctional habits such as bruxism and clenching Patients suffering from periodontitis.
3. Smokers.

Ethical regulation and Informed consents

All patients will undergo an immediate implant placement and the complete treatment plan will be explained to all patients including detailed steps, risks, and expected results. Verbal and written informed consent will be obtained from all patients before the commencement of the study. All steps will be examined and approved by the appropriate ethics committee and have therefore been performed following the ethical standards laid down in the Declaration of Helsinki and the research ethics committee of the Faculty of Dentistry, Minia University.

Pre-surgical phase

1. All selected patients will be screened by comprehensive periodontal examination and full periodontal charts will be obtained. A preoperative cone-beam computed tomography (CBCT) will be performed for each patient who met the inclusion criteria before the surgery to determine bone height and width and decide the implant length and diameter to be placed and to evaluate the underlying bone condition.

Randomization

The study will use simple randomization to allocate patients into 2 groups, each group will be included 10 patients.

Group A: (concentrated growth factor group)

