3. Atraumatic extraction of the tooth or remaining root using periotome, then sequential implant drilling accompanied by copious irrigation will be carried out. then cover screw attached to the implant top by the aid of its driver
4. A sample of venous blood will be withdrawn from the patient and centrifuged without delay according to the preparation protocol of each group.
5. Then the membrane loaded with the bone graft will be applied and condensed around the dental implant filling the gap between the fixture and the walls of the socket.
6. Finally, Tension-free Closure of the wound was achieved using 4/0 vicryl sutures.

Postoperative instructions

1. Routine verbal and written postoperative instructions for periodontal surgery will be given to all patients including ice compression on the surgical site during the first 4 h, a liquid and/or soft food diet for 3 days.
2. As with all surgical procedures, patients will be informed to contact our clinic if any problems will be developed during the postoperative period.
3. The postoperative medications prescribed will be (Amoxicillin+ clavulanic acid*625mg for 7 days) every 8 h or clindamycin** 300 g every 12 h for 7 days for patients allergic to penicillin, and (Ibuprofen*** 600 mg every 12 h for 5 days).
4. The sutures will remain in situ for 2 weeks.

Clinical assessment:

All patients included in the present study will be followed carefully and monitored to motivate the patient for oral hygiene instructions and maintenance of good oral hygiene.

*Augmentin®, GlaxoSmithKline

** Dalacin C®, Pfizer

*** Brufen®, Abbott

Radiographic evaluation

A periapical film with the paralleling technique will be used immediately after the implant placement

And after 9 months CBCT imaging will be used to evaluate:

1- Bony density

2- Marginal bone level.

Statistical analysis:

-All data will be tabulated and analyzed by statistical method.

References

- Araújo, M. G., & Lindhe, J. (2005). Dimensional ridge alterations following tooth extraction. An experimental study in the dog. *Journal of clinical periodontology*, 32(2), 212–218.

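### No masking of the image reading is planned, so both CBCT outcomes may be measured by someone who knows the arm; coded reading would largely remove that risk at little cost

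*Combined protocol and SAP*

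**What the plan says.** - **Outcomes (Radiographic evaluation).** The plan says that "after 9 months CBCT imaging will be used to evaluate" two items, bony density and "Marginal bone level". No software, slice, landmark, region of interest or reader is given for either.
- **Early image (same section).** "A periapical film with the paralleling technique will be used immediately after the implant placement". The plan does not say whether this film is the baseline for bone level.
- **Preoperative CBCT (Pre-surgical phase).** It is taken for each eligible patient to plan the implant. Its role in the outcome comparison is not stated.
- **Allocation (Randomization).** "The study will use simple randomization to allocate patients into 2 groups", and "each group will be included 10 patients". Nothing follows on masking of patients, readers or analysts.
- **Surgery (Surgical Phase, step 4).** "A sample of venous blood will be withdrawn from the patient and centrifuged without delay according to the preparation protocol of each group".
- **Analysis (Statistical analysis).** The whole section reads "All data will be tabulated and analyzed by statistical method".

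The relevant sections are all present in the document. The silence on masking is therefore the plan's own and not a redaction or a fault in text extraction.

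**The concern.** The second aim of the study is to compare PRGF with CGF, and the only outcomes named for that comparison are two readings from one scan. Measurements of this kind probably require judgement about where to place a slice, landmark or region. That is an inference, since no method is stated, but the lack of a method leaves the reader more room, not less.

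If the person measuring knows the arm and leans even slightly towards one product, the lean adds to the between-arm difference. It cannot be separated from a treatment effect afterwards, because it is aligned with the arm in every patient. No choice of test or covariate adjustment repairs it. Protection has to come before the readings are taken.

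**Working it through.** **Step 1. Does the operating team know the arm?** Setting the two preparation protocols side by side:

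| | Group A (CGF) | Group B (PRGF) |
|---|---|---|
| Blood drawn | 10 ml | 30 ml |
| Tubes | no anticoagulant | sodium citrate |
| Centrifugation | four sequential steps | one 8-minute spin |
| Afterwards | clot lifted out with tweezers | calcium chloride, mixed with graft, 40 minutes at 37°C |

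Blood is drawn and processed as a step of the surgery itself, so the team cannot be unaware of the arm.

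**Step 2. Is that team kept away from the readings?** I looked through the whole document for masking, blinding, coded images, an independent examiner or reader agreement. None appears. The supported statement is that the scans may be read by someone who knows the arm.

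**Step 3. What could a reader tendency do?** The plan gives no alpha, test, SD or reader error, so it has no figure of its own to reproduce. The following is illustration only.

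- From the plan: "this study will be conducted on 20 patients indicated for immediate implant placement in the maxillary anterior region", 10 per arm.
- Assumed: two-sample t-test, two-sided 5%, no true difference, and a reader shift of b SD towards one arm.
- Degrees of freedom: 10 + 10 − 2 = 18; critical value t = 2.101.
- Noncentrality: λ = b × √(10/2) = 2.236 b.
- False-positive rate = P(T > 2.101) + P(T < −2.101), with T noncentral t on 18 df and noncentrality λ. The first term is a false finding in favour of the product the reader leans towards.

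| Shift b (SD) | λ | False positive for the favoured product | False-positive rate, both sides |
|---|---|---|---|
| 0 | 0 | 2.5% | 5.0% |
| 0.1 | 0.224 | 4.0% | 5.5% |
| 0.2 | 0.447 | 6.2% | 7.1% |
| 0.3 | 0.671 | 9.3% | 9.7% |
| 0.5 | 1.118 | 18.4% | 18.5% |

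A normal approximation gives 20.0% at 0.5 SD, close to the t result. In every row the estimated difference is also biased by b SD, whether or not a test is significant.

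**Step 4. Would coding hide the arm?** Both arms receive a xenogeneic graft, and the documents give no reason to expect the 9-month image to identify the product. The preoperative scan is different. Inclusion criterion 5 and Group A specify class II sockets, whereas Group B admits class I or class II. The Introduction describes class I as having intact bone walls and class II as having at least one destroyed. If class I sockets entered Group B only, an intact wall on a coded preoperative scan would point to Group B.

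**The case against.** The strongest case on the other side is that silence is not evidence of unmasked reading. That is right as far as it goes. A reader might infer that the scans are read with the allocation known, or that the treating team will read them. The documents support neither statement; they only fail to prevent it.

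A reader might also infer that bias would favour CGF, because the Introduction credits CGF with more growth factors and firmer fibrin. That comparison is with first-generation PRP and second-generation PRF. PRGF is reached only indirectly, through its classification as a pure PRP. The same section also describes PRGF favourably, as a possible stimulant of regeneration that is generally safe and economical. No direction of bias is established.

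The error rates depend wholly on the assumed shift, test and alpha. At 0.1 SD the inflation is only half a percentage point, so the table does not show that the bias is large.

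Finally, coding is not complete protection. With 20 patients, someone who treated them may recognise a case, and the socket-class conflict could reveal the arm.

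All of this limits the wording and the size of the point. None of it supplies the missing safeguard.

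**Conclusion.** The point holds in this form: outcome reading is not masked in the plan, the operating team necessarily knows the arm, and the two CBCT measurements may be made with that knowledge. Any resulting tendency would bias the comparison directly and could not be removed in analysis.

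Its size and direction are unknown. The range of 5.5% to 18.5% for shifts of 0.1 to 0.5 SD rests on assumptions that the documents neither support nor contradict. That measurement involves reader judgement is a reasonable inference and is not stated in the plan.

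It would go too far to say that coding removes the bias. It largely removes it. Masked reading also does nothing for allocation concealment, which is a separate matter. The sponsor should make this change, and it can still be made at any time before the images are measured.

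**What to change.** Add to Radiographic evaluation:

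1. The preoperative and 9-month CBCT files are stripped of patient and arm identifiers and given random codes. The same applies to the immediate postoperative periapical film if it serves as a bone-level baseline.
2. All coded images are measured in random order, at fixed slices and reference points written down beforehand.
3. Codes are broken only after the measurement file is locked.
4. Where existing staff allow, the reader is a team member who did not operate, prepare the concentrates, hold the allocation list or follow the patients.

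Reconcile the socket class given in inclusion criterion 5 and Group A with that given in Group B. Until that is done, read the 9-month scans without the preoperative scans alongside where possible.

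The number of patients stays at 20 and no scan or visit is added. The cost is probably a few hours of file coding and scheduling. This is an assumption, because the documents do not describe staffing. If only the operator is available to read, items 1 to 3 still help, but recognition of individual cases remains possible and should be acknowledged in the report.
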